8.2. Correlative lab study

Patients will be offered the opportunity to participate in the correlative components of the study, however participation will be optional. Whole blood, plasma, and serum samples will be drawn within 2 weeks prior to radiation therapy and then drawn 3, 6, 9 and 12 months after radiation therapy.

Platelet-poor plasma will be obtained for cytokine assays; serum samples will be used for, cell death assays and other markers as indicated; buffy coat will be used for genomic studies including methylation analysis. Plasma TGF- β 1 will be measured by molecular specific Enzyme Linked Immune Sandwich Assay (ELISA). The levels of plasma cytokines will be measured by ready to use kits, such as LINCOPlex (microsphere-based sandwich immunoassay) for the concentrations of 29 proinflammatory cytokines, including G-CSF, IL-1 α , IL-1 β , IL-1ra, IL-6, IL-8, IP-10, MCP-1, MIP-1, TGF- α , and TNF- α . RILT will be diagnosed and graded based on CTCAE 4. For genomic studies, we will focus our efforts on (but not limited to) global SNP and DNA methylation as well as SNP and methylation analysis of TGF β 1, tissue plasminogen activator (tPA) and angiotensinconverting enzyme (ACE), which are associated with radiation-induced thoracic toxicity such as radiation induced lung injury. Genetic variations within functional locus of these genes will be assessed for in each patient by using gene specific PCR technology. Such SNP studies will be performed using polymerase chain reaction (PCR) and allele specific primers. Genome wide methylation profiling will be performed using the Illumina Infinium HumanMethylation450 BeadChip array which examines the methylation status of 485,577 CpG sites distributed throughout the whole genome, covering 96% of CpG islands and 99% of RefSeq genes. Methylation status of select genes of interests will also be validated using pyrosequencing. Bioinfomatic methodology may be applied for data analysis. Blood markers (cytokine and genomics)

during early course of treatment will be correlated to clinical outcome including tumor control.

Blood (whole blood, plasma and serum) will be processed by the UWCCC BioBank (Translational Science BioCore). 30 ml peripheral blood (two 10 ml EDTA tubes and one 10 ml SST tube) will be taken from each patient at each time point.

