10.2.2. Global measures of change

10.2.2.1. Pulmonary Function Tests. Changes in patient self-assessment, forced vital capacity (FVC), forced expiratory volume in one second (FEV1), and diffusion lung capacity for carbon monoxide (DLCO). All metrics will be evaluated at 3, 6, and 12 months post-RT in comparison to values pre-RT.

10.2.2.2. Inflammation. Plasma TGF- β 1 will be measured by molecular specific Enzyme Linked Immune Sandwich Assay (ELISA). The levels of plasma cytokines will be measured by ready to use kits for the concentrations of 29 proinflammatory cytokines, including G-CSF, IL-1 α , IL-1 β , IL-1ra, IL-6, IL-8, IP-10, MCP-1, MIP-1, TGF- α , and TNF- α .

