11. STATISTICAL CONSIDERATIONS

11.1. Study Design/Endpoints

The primary endpoint of this study will be the ratio of the tissue elasticity map following RT to the elasticity map before RT (i.e., the Jacobian ratio of (post RT /pre RT)) calculated from 4DCT at 3 months post-RT. Based on the randomness of our measurement technique, diminished expansion is defined as a Jacobian ratio <0.94 (i.e., less than 94% of the pre-RT value). Data for the analysis will consist of the voxel-specific ratios of tissue elasticity measures from scans being compared. The primary and secondary endpoints at 3, 6, and 12 months post-RT include: (i) the volume of lung where diminished expansion occurs (Jacobian ratio (post RT /pre RT) <0.94), (ii) the volume of lung where expansion is improved (Jacobian ratio (post RT /pre RT) >1.06), (iii) the volume of lung where “meaningful” expansion occurs (Jacobian post-RT > 1.1), and (iv) clinically observed pulmonary toxicity determined by PFT endpoints, and (v) changes in inflammation as determined from blood serum.

Some subjects may have multiple sites of disease treated within the thorax. Since these subjects will be treated at all sites with either the control (Arm 1) or experimental (Arm 2) treatment plan, and since the primary endpoint of the study is the assessment of normal lung tissue response to delivered radiation, these subjects represent a single sample within our analysis.

Power analysis shows the planned enrollment of 60 subjects per cohort will ensure 90% power to detect mean difference of 4% in the lung tissue elasticity (percentage of the lung with a Jacobian ratio post-RT/pre RT < 0.94), based on 6.3% deviation in this measure from 13 subjects in our preliminary data. If the normality assumptions of ANOVA are not satisfied, nonparametric rank-based tests will be used instead. All statistical tests will be two-sided and assessed for significance at the 5% level, and will be performed by the UW-Madison Department of Biostatistics and Medical Informatics.

Update as of 2/3/2021: The statistics are based on 30 subjects reaching the 3 month followup time point. To date 106 have been enrolled but 14 did not complete the 3 month imaging time point. Therefore we are adding numbers to replace those subjects and to allow an additional 5 subjects to ensure we complete the protocol and meet the study objectives.

REFERENCES

1. American Cancer Society. *Cancer Facts & Figures 2015*. Atlanta: American Cancer Society; 2015.

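### Section 11.1 sets a flat 5% level for all tests with no multiplicity rule, so the blood-marker endpoint alone would be expected to give about six false positives in 120 tests

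*Combined protocol and SAP*

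**What the plan says.** Section 11.1 fixes one significance rule: "All statistical tests will be two-sided and assessed for significance at the 5% level". It makes no exception. The same section introduces its endpoint list with "The primary and secondary endpoints at 3, 6, and 12 months post-RT include" and then names five groups:

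- (i) volume of lung with diminished expansion
- (ii) volume with improved expansion
- (iii) volume with meaningful expansion
- (iv) pulmonary toxicity by PFT endpoints
- (v) "changes in inflammation as determined from blood serum"

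Section 10.2.2.2 gives the content of the inflammation endpoint: TGF-beta1 by ELISA, and kits for "the concentrations of 29 proinflammatory cytokines". Section 8.1 compares the blood markers with baseline at 3, 6, 9 and 12 months after RT.

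Section 8.2, an optional correlative study, adds a methylation array that "examines the methylation status of 485,577 CpG sites distributed throughout the whole genome". It says cytokine and genomic markers will be correlated with clinical outcome, and it permits bioinformatic methods without naming one. The Section 8 heading closes further sample collection. Nothing cancels analysis of the samples already frozen.

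The primary metric (Sections 1.1 and 10.1) is the amount of lung with a Jacobian ratio below 0.94 at 3 months.

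**The concern.** A 5% level suits one pre-specified comparison. Applied unchanged to a panel of 30 markers at several times, it will mark some of them significant by chance, and the plan gives the reader no way to tell these from real changes. Secondary objective 2 uses the PFT and blood-marker results, and also correlates them with regional dose and with the elasticity maps, so the true number of tests is probably larger than the count below. What is at stake is the credibility of the secondary and correlative claims. The treatment comparison on the primary endpoint is not at stake.

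**Working it through.** The plan states no familywise error rate or false-positive count, so there is no figure of its own to reproduce. The check counts tests and applies the stated level.

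**Inputs**
- Level: 0.05, two-sided (Section 11.1).
- Blood markers: 29 + 1 = 30 (Section 10.2.2.2). Section 11.1 speaks of serum and Section 10.2.2.2 of plasma; I take them as the same endpoint.
- Post-RT times: 3 (Section 11.1) or 4 (Section 8.1).
- Elasticity endpoints (i) to (iii): 3 measures at 3 times = 9.
- PFT measures FEV1, FVC and DLCO: 3 at 3 times = 9. Patient self-assessment is left out.
- Array coverage: 485,577 sites (Section 8.2).

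**Formula.** Expected false positives = number of true null hypotheses × 0.05. This does not require the tests to be independent.

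**Blood markers, all nulls true**
- One time: 30 × 0.05 = 1.5.
- Three times: 30 × 3 = 90 tests; 90 × 0.05 = 4.5.
- Four times: 30 × 4 = 120 tests; 120 × 0.05 = 6.0.

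**All listed endpoints, all nulls true**
- Three blood draws: 9 + 9 + 90 = 108 tests; 108 × 0.05 = 5.4.
- Four blood draws: 9 + 9 + 120 = 138 tests; 138 × 0.05 = 6.9.
- Each fractionation cohort tested separately: 2 × 5.4 = 10.8 to 2 × 6.9 = 13.8.

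These totals include the primary test itself (endpoint (i) at 3 months). Removing it lowers each single-pass total by 0.05.

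**Methylation array, only if every site were tested once at a flat 5%**
- All sites null: 485,577 × 0.05 = 24,279.
- 90% of sites null: 485,577 × 0.9 × 0.05 = 21,851.

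**Primary comparison.** Section 11.1 sizes the trial per cohort but does not say whether the arms are compared once or within each cohort. Two independent tests at 5% give 1 − 0.95² = 0.0975, or 9.75%.

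**The case against.** The strongest reply is that the sentence fixes sidedness and level but does not say that p-values go unadjusted. Benjamini-Hochberg adjusted p-values judged at 5% would satisfy it. That is right as far as it goes: the sentence does not forbid adjustment. But nothing in the document provides for one, and an analyst following the plan as written would compare each raw p-value with 0.05.

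A second reply is that unadjusted secondary testing in a single-centre trial with one primary metric is mainly a matter of labelling. This also has force, and it limits the seriousness of the point. The plan does not supply the label, however.

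A reader might go further and infer that the 5% rule governs all 485,577 methylation sites, so that following the plan would produce thousands of false positives. The documents do not support that. Methylation is not among endpoints (i) to (v), nor in secondary objective 2. The figure of 485,577 is the array's coverage, not a planned number of tests. Section 8.2 leaves the analysis open, names candidate genes and adds pyrosequencing validation of selected genes. What stands is that Section 8.2 gives no error-rate rule of its own.

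A reader might also take five endpoint groups at three times in two cohorts as 30 tests and quote 1 − 0.95³⁰ = 79% as the chance of at least one false secondary success. That figure should not be used. It includes the primary endpoint and counts groups (iv) and (v) as single tests although each holds several measures. It also assumes independence between measures taken from the same maps in the same subjects, and it is not an upper bound.

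**Conclusion.** The point holds for the secondary and correlative tests. Under the stated rule, the blood-marker endpoint alone carries about 4.5 to 6 expected false positives. The listed endpoints together carry about 5 to 7, or about 11 to 14 if the two cohorts are tested separately. These counts assume that every null is true and that each measure is tested once per time; they fall in proportion to the share of real effects. The further correlations in secondary objective 2 are not counted.

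The array figure of about 24,000 is conditional on a site-by-site analysis at 5%, which the plan does not state.

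The secondary and correlative tests do not inflate the error of the 3-month primary comparison, so the primary conclusion is unaffected by them. The one multiplicity question that touches the primary is whether it is tested once or once per cohort, and the plan should answer it.

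**What to change.** Amend Section 11.1, and cross-refer to it from Section 8.2, as follows:

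- Limit the 5% significance rule to the 3-month primary comparison. State whether this is one test or one per fractionation cohort and, if two, how the 9.75% is handled.
- Declare blood-marker findings by Benjamini-Hochberg false discovery rate, for example at 5%, taking the 30 markers and all their time points as one family. Apply the same rule, as a separate family, to any array-wide methylation analysis.
- Report endpoints (ii) to (iv), and the 6- and 12-month values of endpoint (i), as estimates with 95% confidence intervals, labelled supportive.

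The cost is SAP wording and routine analysis code. No patients, scans or samples are added. The downside is that fewer markers will be called significant: with 120 tests, a marker that is the only finding would need p ≤ 0.05/120 = 0.00042.

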APPENDIX A: PERFORMANCE STATUS CRITERIA

ECOG Performance Status Scale		Karnofsky Performance Scale	
Grade	Descriptions	Percent	Description
0	Normal activity. Fully active, able to carry on all pre-disease performance without restriction.	100	Normal, no complaints, no evidence of disease.
		90	Able to carry on normal activity; minor signs or symptoms of disease.
1	Symptoms, but ambulatory. Restricted in physically strenuous activity, but ambulatory and able to carry out work of a light or sedentary nature (e.g., light housework, office work).	80	Normal activity with effort; some signs or symptoms of disease.
		70	Cares for self, unable to carry on normal activity or to do active work.
2	In bed <50% of the time. Ambulatory and capable of all self-care, but unable to carry out any work activities. Up and about more than 50% of waking hours.	60	Requires occasional assistance, but is able to care for most of his/her needs.
		50	Requires considerable assistance and frequent medical care.
3	In bed >50% of the time. Capable of only limited self-care, confined to bed or chair more than 50% of waking hours.	40	Disabled, requires special care and assistance.
		30	Severely disabled, hospitalization indicated. Death not imminent.
4	100% bedridden. Completely disabled. Cannot carry on any self-care. Totally confined to bed or chair.	20	Very sick, hospitalization indicated. Death not imminent.
		10	Moribund, fatal processes progressing rapidly.
5	Dead.	0	Dead.

**APPENDIX B: Radiation Therapy Oncology Group Acute toxicity
(baseline, during RT, 3 month post-RT)**

Lung	0	None
	1	Mild symptoms of dry cough or dyspnea on exertion
	2	Persistent cough requiring narcotic, antitussive agents; or Dyspnea with minimal effort but not at rest
	3	Severe cough unresponsive to narcotic antitussive agent; or Dyspnea at rest; or, Clinical or radiographic evidence of pneumonitis; or, Intermittent oxygen or steroids may be required
	4	Severe respiratory insufficiency; or, Continuous oxygen or assisted ventilation required
	5	Death

Esophageal	0	None
	1	Mild dysphagia or odynophagia; or, Requires topical anesthetic or non-narcotic analgesics; or, Requires soft diet
	2	Moderate dysphagia or odynophagia; or, Requires narcotic analgesics; or, Requires puree or liquid diet
	3	Severe dysphagia or odynophagia with dehydration or weight loss (>15% from pretreatment baseline) requiring nasogastric feeding; or, I.V. fluids; or, Hyperalimentation
	4	Complete obstruction, ulceration, perforation, or fistula
	5	Death

Weight loss	0	None
	1	5 to <10% from baseline; intervention not indicated
	2	10 - <20% from baseline; nutritional support indicated
	3	≥ 20% from baseline; tube feeding or TPN indicated

**APPENDIX C: Radiation Therapy Oncology Group Late toxicity
(6 months post-RT and beyond)**

Lung	0	None
	1	Mild symptoms (dry cough); or, Slight radiographic appearances
	2	Moderate symptomatic fibrosis or pneumonitis (severe cough); or, Low-grade fever; or, Patchy radiographic appearance
	3	Severe symptomatic fibrosis or pneumonitis; or, dense radiographic changes
	4	Severe respiratory insufficiency; or, continuous oxygen or assisted ventilation required
	5	Death

Esophageal	0	None
	1	Mild fibrosis; or, slight difficulty in swallowing solids (no pain on swallowing)
	2	Unable to take solid food normally; or, Swallowing semi-solid food Dilation indicated
	3	Severe fibrosis; or, Able to swallow only liquids; Pain upon swallowing; Dilation required
	4	Necrosis/perforation
	5	Death

Skin	0	None
	1	Slight atrophy; or, Pigmentation change; or, Some hair loss
	2	Patchy atrophy; or, Moderate telangiectasia; or, Total hair loss
	3	Marked atrophy; or, Gross telangiectasia
	4	Ulceration

Subcutaneous tissue	0	None
	1	Slight induration (fibrosis) and loss of subcutaneous fat
	2	Moderate fibrosis but asymptomatic; or, Slight field contracture (<10% linear reduction)
	3	Severe induration and loss of subcutaneous tissue; or, Field contracture (>10% linear measurement)
	4	Necrosis

Radiation Therapy Oncology Group Late toxicity

(6 months post-RT and beyond)

Spinal cord	0	None
	1	Mild L'Hermitte's syndrome
	2	Severe L'Hermitte's syndrome
	3	Objective neurological findings at or below cord level treatment
	4	Mono, para, quadriplegia

Heart	0	None
	1	Asymptomatic or mild symptoms; or, Transient T-wave inversion & ST changes; Sinus tachycardia >110 (at rest)
	2	Moderate angina on effort; or, Mild pericarditis (normal heart size); or, Persistent abnormal T-wave and ST changes; or, Low ORS
	3	Severe angina; or Pericardial effusion; or Constrictive pericarditis; or Moderate heart failure; or Cardiac enlargement; or EKG abnormalities
	4	Tamponade; or Severe heart failure; or Severe constrictive pericarditis

Bone Fracture	0	None
	1	Asymptomatic; clinical or diagnostic observations only; intervention not indicated
	2	Symptomatic but non-displaced; immobilization indicated
	3	Severe symptoms; displaced or open wound with bone exposure; disabling; operative intervention indicated
	4	Life-threatening consequences; urgent intervention indicated

APPENDIX D: RTOG PULMONARY FUNCTION TOXICITY CRITERIA
(baseline and at 3, 6 and 12 months; coinciding with 4DCT scans)

The SBRT Pulmonary Toxicity Scale

Adverse Event	Grade				
	1	2	3	4	5
FEV-1 Decline	0.90-0.75 times the patient's baseline value	<0.75-0.50 times the patient's baseline value	<0.50-0.25 times the patient's baseline value	<0.25 times the patient's baseline value	Death
Forced Vital Capacity Decline	0.90-0.75 times the patient's baseline value	<0.75-0.50 times the patient's baseline value	<0.50-0.25 times the patient's baseline value	<0.25 times the patient's baseline value	Death
DLCO Decline	0.90-0.75 times the patient's baseline value	<0.75-0.50 times the patient's baseline value	<0.50-0.25 times the patient's baseline value	<0.25 times the patient's baseline value	Death

APPENDIX E: PATIENT SELF ASSESSMENT CRITERIA

Modified Borg Scale

G. Borg, Psychophysical bases of perceived exertion, Med Sci Sports Exerc, 14 (1982), pp. 377–381

0	No breathlessness* at all
0.5	Very, very slight (just noticeable)
1	Very slight
2	Slight breathlessness
3	Moderate
4	Somewhat severe
5	Severe breathlessness
6	
7	Very severe breathlessness
8	
9	Very, very severe (almost maximal)
10	Maximal

Figure 1

Modified Borg scale. (Note: The word “breathlessness” was added in our version of the scale for clarification.) (From Burdon JGW, Juniper EF, Killian KJ, Hargrave FE, Campbell EJM. The perception of breathlessness in asthma. Am Rev Respir Dis 1982;126:825-8. Official Journal of the American Thoracic Society. © by the American Lung Association.)

APPENDIX F: UWCCC DATA SAFETY MONITORING PLAN

Oversight And Monitoring Plan

The UWCCC Data and Safety Monitoring Committee (DSMC) is responsible for the regular review and monitoring of all ongoing clinical research in the UWCCC. A summary of DSMC activities are as follows:

- Reviews all clinical trials conducted at the UWCCC for subject safety, protocol compliance, and data integrity.
- Reviews all Serious Adverse Events (SAE) requiring expedited reporting, as defined in the protocol, for all clinical trials conducted at the UWCCC, and studies conducted at external sites for which UWCCC acts as an oversight body.
- Reviews all reports generated through the UWCCC DSMS elements (Internal Audits, Quality Assurance Reviews, Response Reviews, Compliance Reviews, and Protocol Summary Reports)
- Notifies the protocol Principal Investigator of DSMC decisions and, if applicable, any requirements for corrective action related to data or safety issues.
- Notifies the CRC of DSMC decisions and any correspondence from the DSMC to the protocol Principal Investigator.
- Works in conjunction with the UW Health Sciences IRB in the review of relevant safety information as well as protocol deviations, non-compliance, and unanticipated problems reported by the UWCCC research staff.
- Ensures that notification is of SAEs requiring expedited reporting is provided to external sites participating in multi-institutional clinical trials coordinated by the UWCCC.

Monitoring And Reporting Guidelines

UWCCC quality assurance and monitoring activities are determined by study sponsorship and risk level of the protocol as determined by the PRMC. All protocols (including Intervention Trials, Non-Intervention Trials, Behavioral and Nutritional Studies, and trials conducted under a Training Grant) are evaluated by the PRMC at the time of committee review. UWCC monitoring requirements for trials without an acceptable external DSMB are as follows:

Intermediate Monitoring Protocols subject to intermediate monitoring generally include UW Institutional Phase I/II and Phase II Trials. These protocols undergo review of subject safety at regularly scheduled DOWG meetings where the results of each subject's treatment are discussed and the discussion is documented in the DOWG meeting minutes. The discussion includes the number of subjects enrolled, significant toxicities, dose adjustments, and responses observed. Protocol Summary Reports are submitted on a semi-annual basis by the study team for review by the DSMC.

Review and Oversight Requirements

Serious Adverse Events requiring reporting within 24 hours (as described in the protocol) must also be reported to the Data and Safety Monitoring Committee (DSMC) Chair via an email to [contact] within one business day. The OnCore SAE Details Report must be submitted along with other report materials as appropriate (NCI AdEERS form or FDA Medwatch Form #3500 and/or any other documentation available at that time of initial reporting). The DSMC Chair will review the information and determine if immediate action is required. Within 10 working days, all available subsequent SAE documentation must be submitted electronically along with a 24 hour follow-

up SAE Details Report and a completed UWCCC SAE Routing Form to [contact]. All information is entered and tracked in the UWCCC database. The Principal Investigator notifies all investigators involved with the study at the UWCCC, the IRB, the sponsor, and the funding agency and provides documentation of these notifications to the DSMC. If the SAE occurs on a clinical trial in which the UW PI serves as the sponsor-investigator, the PI reviews the event to determine whether the SAE requires reporting to the FDA and other participating investigators. For a multiple-institutional clinical trial the PI is responsible for ensuring SAEs are reported to the FDA as well as to all participating investigators

Serious Adverse Event-Reported within 10 Days

Serious Adverse Events requiring reporting within 10 days (as described in the protocol) must also be reported to the Data and Safety Monitoring Committee (DSMC) Chair via an email to [contact]. The OnCore SAE Details Report must be submitted along with other report materials as appropriate (NCI AdEERS form or FDA Medwatch Form #3500 and/or any other documentation available at that time of initial reporting). The DSMC Chair will review the information and determine if further action is required. All information is entered and tracked in the UWCCC database. The Principal Investigator notifies all investigators involved with the study at the UWCCC, the IRB, the sponsor, and the funding agency and provides documentation of these notifications to the DSMC. If the SAE occurs on a clinical trial in which the UW PI serves as the sponsor-investigator, the PI reviews the event to determine whether the SAE requires reporting to the FDA and other participating investigators. For a multiple-institutional clinical trial the PI is responsible for ensuring SAEs are reported to the FDA as well as to all participating investigators.

Sponsor-Investigator Responsibilities for SAE Review

In the event the UWCCC Principal Investigator is acting as the Sponsor-Investigator (i.e., the PI holds the IND), the PI assumes responsibilities of the study sponsor in accordance with FDA 21 CFR 312.32. In this capacity, the UWCCC PI reviews all reports of serious adverse events occurring on the study at the UWCCC and participating external sites and makes a determination of 1) suspectedness (i.e., whether there is a reasonable possibility that the drug caused the AE); and 2) unexpectedness in the context of theis study. SAE with suspected causality to study intervention deemed unexpected are reported as IND safety Reports by the UWCCC PI to the FDA, all participating investigators on the study, within 15 calendar days. All fatal or life-threatening SAE that are unexpected and have suspected causality to the study intervention will be reported by the UWCCC PI to the FDA, all participating investigators on the study within 7 calendar days.

Study Progress Review

Protocol Summary Reports (PSR) are required to be submitted to the DSMC in the timeframe determined by the risk level of the study (quarterly; semi-annually; or annually). The PSR provides a cumulative report of SAEs, as well as instances of non-compliance, protocol deviations, and unanticipated problems, toxicities and responses that have occurred on the protocol in the timeframe specified. PSRs for those protocols scheduled for review are reviewed at each DSMC meeting.

Protocol Summary Reports enable DSMC committee members to assess whether significant benefits or risks are occurring that would warrant study suspension or closure. This information is evaluated by the DSMC in conjunction with other reports of quality assurance activities (e.g., reports from Internal Audits, Quality Assurance Reviews, etc.) occurring since the prior review of the protocol by the DSMC. Additionally, the DSMC requires the study team to submit external DSMB or DSMC reports, external

monitoring findings for industry-sponsored studies, and any other pertinent study-related information.

In the event that there is significant risk warranting study suspension or closure, the DSMC will notify the PI of the DSMC findings and ensure the appropriate action is taken for the protocol (e.g., suspension or closure). The DSMC ensures that the PI reports any temporary or permanent suspension of a clinical trial to the sponsor (e.g., NCI Program Director, Industry Sponsor Medical Monitor, Cooperative Group Study Chair, etc.) and other appropriate agencies. DSMC findings and requirements for follow-up action are submitted to the CRC

Expedited Reporting Of Serious Adverse Events

Depending on the nature, severity, and attribution of the serious adverse event an SAE report will be phoned in, submitted in writing, or both according to Table below. All serious adverse events must also be reported to the UWCCC Data and Safety Monitoring Committee Chair. All serious adverse events must also be reported to the UW IRB (if applicable), and any sponsor/funding agency not already included in the list. Determine the reporting time line for the SAE in question by using the following table. Then refer to sections A and B below if the SAE occurred at the UWCCC or sections C and D if the SAE occurred at 1 South Park, Johnson Creek, or a WON Site.

SAE Requiring /24/ Hour Reporting Occurs at UWCCC:

1. Report to the UWCCC:

Reference the **SAE SOP** (Standard Operating Procedure) and the **SAE Reporting Workflow for DOWGs** on the UWCCC website (<http://www.uwccc.wisc.edu>) for specific instructions on how and what to report to the UWCCC for /24/ hour initial and follow-up reports. **A follow-up report is required to be submitted within 5 days of the initial /24/ hour report.**

For this protocol, the following UWCCC entities are required to be notified:

- a) [contact]
- b) *[name]., UWCCC PI*
- c) *[name], UWCCC Radiotherapy PM*
- d) Any other appropriate parties listed on the SAE Routing Form (for follow-up reports only)

2. Report to the IRB:

Consult the UW-IRB website for reporting guidelines

SAE Requiring /10/ Day Reporting Occurs at UWCCC:

1. Report to the UWCCC:

Reference the **SAE SOP** and the **SAE Reporting Workflow for DOWGs** on the UWCCC website (<http://www.uwccc.wisc.edu>) for specific instructions on how and what to report to the UWCCC for /10/ day reports.

For this protocol, the following entities are required to be notified:

- a) [contact]
- b) Any appropriate parties listed on SAE Routing Form

2. Report to the IRB:

Consult the UW-IRB website for reporting guidelines.

Other Reporting Requirements

Reporting to the FDA

Serious Adverse Events occurring on studies on which a UW PI is acting as sponsor-investigator must be reported to the FDA within the appropriate time frame. Mandatory and voluntary reporting guidelines and instructions are outlined on the FDA website:

<http://www.fda.gov/Safety/MedWatch/HowToReport/default.htm>

Table 1. Expedited reporting requirements for adverse events that occur within 30 days of the last dose of protocol RT and thought to be at least possibly related to protocol RT

FDA Reporting Requirements for Serious Adverse Events (21 CFR Part 312)

NOTE: Investigators MUST immediately report to the PI, UWCCC and UW IRB per policy ANY Serious Adverse Events, whether or not they are considered related to the investigational agent(s)/intervention (21 CFR 312.64). FDA Med Watch (3500A) will be submitted for grade 4 and 5 events at the discretion of the sponsor-investigator.

An adverse event is considered serious if it results in ANY of the following outcomes:

- Death.
- A life-threatening adverse event.
- An adverse event that results in inpatient hospitalization or prolongation of existing hospitalization for \geq 24 hours.
- A persistent or significant incapacity or substantial disruption of the ability to conduct normal life functions.
- A congenital anomaly/birth defect.

Important Medical Events (IME) that may not result in death, be life threatening, or require hospitalization may be considered serious when, based upon medical judgment, they may jeopardize the patient or subject and may require medical or surgical intervention to prevent one of the outcomes listed in this definition (FDA, 21 CFR 312.32; ICH E2A and ICH E6).

ALL SERIOUS adverse events that meet the above criteria* MUST be immediately reported to the UWCCC within the timeframes detailed in the table below:

Hospitalization	Grade 1 and Grade 2 Timeframes	Grade 3 Time Frames	Grade 4 & 5 Timeframes
Resulting in hospitalization \geq 24 hrs	Not required	10 Calendar Days	24 Hour; 5 Calendar Days
Not resulting in Hospitalization \geq 24 hrs	Not required	10 Calendar Days	

- See section 8.0, appendix B, C and D for listing of toxicities
- Grade 3 toxicites resulting in hospitalization with attribution of probably or definitely related to chemotherapy will be exempt from expedited reporting

Expedited AE reporting timelines are defined as:

- **24-Hour; 5 Calendar Days** – The AE must initially be reported within 24 hours of learning of the AE, followed by a complete expedited report within 5 calendar days of the initial 24-

hour report.

- **10 Calendar Days** – A complete expedited report on the AE must be submitted within 10 calendar days of learning of the AE

¹ Serious adverse events that occur more than 30 days after the RT dose and have an attribution of possible, probable, or definite related to radiation or other study procedures (4DCT and PFTs) require reporting as follows:

Expedited 24-hour notification followed by complete report within 10 working days for:

- All Grade 4, and 5 AEs
